## 7.4 Stopping Rules

The toxicity criteria are based on the WHO toxicity scale, with added assessments pertaining to ocular AEs (located in the Manual of Procedures). Dose-limiting toxicity (DLT) will be defined as any irreversible Grade 3 or higher toxicity, or any reversible Grade 4 toxicity, that is possibly or probably related to AAV2-hCHM. Irreversible toxicities are defined as those that persist at the same (or higher) grade for more than seven days; reversible toxicities are those resolving in seven or fewer days.

If DLT is experienced, further subject enrollment will be delayed pending consultation with the DSMB. If a subject experiences any DLT, the DSMB will assist in determining whether additional subjects should be enrolled at the same dose level, or at a lower dose level. If two subjects of a dose group develop limiting toxicity, possibly or probably attributable to the vector, the maximum tolerated dose (MTD) will have been reached. In the event this occurs in Dose Group 2, additional subjects may be enrolled to the group just below the MTD, *i.e.* Dose Group 1.

If a single occurrence of Grade 4 toxicity, excluding toxicities covered under the category "General", or death of a subject occurs and is deemed possibly or probably related to the AAV2-hCHM, the Sponsor will halt enrollment and notify the DSMB and FDA. Further enrollment and/or vector administrations will be conducted only after FDA and the Sponsor confer to determine that the IND is not on clinical hold, and the DSMB agrees to continue enrollment. Study visits for subjects that have already received AAV2-hCHM will continue per protocol.

The Sponsor or designee will report all SAEs and AEs to the DSMB, FDA, NIH OBA, and to Principal Investigators (who will in turn notify the IRBs/Institutional Ethics Committees (IECs) of record) within the required reporting timeframes. In addition to the stopping rules outlined above and based on the toxicity criteria table (located in the Manual of Procedures), the Sponsor will respond to recommendations of the DSMB.

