#### 8.8 Reporting Timeframes

The Investigators are responsible for notifying the Sponsor or designee of all AEs, other unanticipated problems related to research, and pregnancy occurrences and outcomes in accordance with the following timeline:

Type of AE	Initial Notification (Phone, Email)	Written Report
All serious AEs, including serious SARs	24 hours	The investigator (or delegate) must submit the SAE report forms (initial and follow-up) within 24 hours to the Sponsor/designee. Local telephone and fax number for reporting from each specific participating country is provided in the Investigator Study Manual. If the minimum requirements for reporting are known, the investigator should notify Spark immediately and not wait for additional information to fully document the event. Follow-up reports will be submitted by the investigator to Spark at appropriate intervals until the SAE has resolved or, in the case of permanent impairment, until it has stabilized.
Other unanticipated problems or reportable events related to research and pregnancy occurrences and outcomes	N/A	Within 5 business days
All other AEs	N/A	Summary of AEs reported at time of continuing review As needed for sponsor reporting requirements (FDA & NIH/OBA annual reports and DSMB reports) or as specified in MOP

All AEs must be entered in the appropriate section of the CRF. To improve the quality and consistency of AE data, Investigators should observe the following general guidelines:

• Standard English medical terminology should be used rather than colloquial expressions or abbreviations.

- Whenever possible, the AE should be evaluated and reported as a diagnosis rather than as individual signs or symptoms. If a definitive diagnosis is not possible, the individual signs and symptoms should be recorded.
- If an AE requires a surgical or diagnostic procedure, the illness leading to the procedure should be recorded as the AE, not the procedure itself.

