For SAEs, the initial notification should include all available information requested on the SAE Form; the initial notification must be followed by written documentation, which includes all information including causality assessment from the Principle Investigator. The SAE Form will collect data surrounding the event, *e.g.*, the nature of the symptom(s), time of onset in relation to initiation of investigational product, duration, severity, and whether or not treatment was administered for the symptoms experienced. The Investigator's assessment of the probable cause of the event will also be included. A physician will examine subjects who experience an SAE or a medical emergency situation as soon as possible. The physician in attendance will do whatever is medically necessary for the safety and well-being of the subject. The subject will remain under observation as long as medically indicated in the opinion of the Investigator. Appropriate lab studies will be conducted until all parameters return to normal or are otherwise explained. The SAE will be followed until resolved or until medically stabilized. In a medical emergency requiring immediate attention, study site staff will provide appropriate medical care, according to current standards of care. The Investigator or his/her designee should contact the Sponsor or designee Medical Monitor. The Sponsor or designee will notify the appropriate federal regulatory authorities.

If an SAE has not resolved at the time of the initial report, a follow-up report including all relevant new or reassessed information (*e.g.*, concomitant medication, medical history) should be submitted to the Sponsor or designee. All SAEs should be followed until either resolved or stable. The Medical Monitor and the independent DSMB will review all AEs.

Investigator safety reports must be prepared for suspected unexpected serious adverse reactions (SUSARs) according to local regulatory requirements and Sponsor policy, and forwarded to Investigators as necessary. An Investigator who receives an investigator safety report describing an SAE or who receives other specific safety information (e.g., summary or listing of SAEs) from the Sponsor will review and then file it along with the Investigator's Brochure and will notify the IRB/IEC if appropriate according to local regulatory reporting requirements.

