Prior to implementation, any amendments to the protocol that have subject safety implications must be approved by the IRB and DSMB, and submitted to the IND on file with FDA. Measures that are critical for subject safety may be implemented simultaneously with reporting to the IRB, DSMB, and FDA. Any manuscript, abstract, or presentation will be available to all the Investigators involved in this study, as well as the DSMB as described above, for review prior to submission.

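### The single Grade 4 or death halt in Protocol 7.4 does not reach harm attributed only to the administration procedure or anesthesia; the gap is narrow and cheap to close

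*Protocol*

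**What the plan says.** Protocol 7.4 has three rules that an event can trigger.

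- **DLT.** Grade 3 or higher toxicity lasting more than seven days, or "any reversible Grade 4 toxicity, that is possibly or probably related to AAV2-hCHM". One DLT delays enrollment while the DSMB is consulted.
- **MTD.** Two subjects in a dose group with limiting toxicity attributable to the vector.
- **Single-event halt.** The sentence opens "If a single occurrence of Grade 4 toxicity, excluding toxicities covered under the category" General, and continues "or death of a subject occurs and is deemed possibly or probably related to the AAV2-hCHM". Dosing resumes only after FDA and the Sponsor have conferred and the DSMB agrees.

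Each rule requires attribution to the product. Protocol 8.6 nevertheless has the investigator rate every adverse event separately against the administration procedure, the product and the study measures. Protocol 9.4.2, under General Anesthesia Risks, names seizure, coma and death as rare events of anesthesia and surgery.

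Other provisions carry no attribution limit:

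- 7.4: "The Sponsor or designee will report all SAEs and AEs to the DSMB, FDA, NIH OBA", and "the Sponsor will respond to recommendations of the DSMB".
- 8.8: "The investigator (or delegate) must submit the SAE report forms (initial and follow-up) within 24 hours to the Sponsor/designee", and "The Medical Monitor and the independent DSMB will review all AEs".
- 9.4.1: "Measures that are critical for subject safety may be implemented simultaneously with reporting to the IRB, DSMB, and FDA".
- 3.2 and SAP 8: escalation to Dose Group 2 needs DSMB approval after at least 30 days of data on the prior cohort.

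**The concern.** Vector delivery requires general anesthesia and subretinal surgery, and the protocol accepts that these can, rarely, kill or seriously injure. The halt in 7.4 is nevertheless worded by product attribution alone. If a subject died and the death was put down to anesthesia, no rule in 7.4 would require the next injection to wait. If the same death were deemed possibly related to AAV2-hCHM, dosing would stop until FDA, the Sponsor and the DSMB had acted. A mandatory hold would then turn on how the cause was divided between surgery and product, which is hard to judge soon after an event. Section 7.4 also does not say who makes that judgment: 8.6 records the investigator's opinion, and 8.3 gives the sponsor a causality judgment as well.

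**Working it through.** The plan states no operating characteristic for these rules, so there is no figure to reproduce. The check is a reading of 7.4 against 8.6, followed by a count of exposure.

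**1. Which deaths or Grade 4 harms fall outside the halt**

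| Event | Product rating available under 8.6 | Halt in 7.4 |
|---|---|---|
| Anesthetic or surgical harm before any vector is given | *Unlikely*: it cannot follow administration of the product | Not triggered |
| Harm after injection, timing judged reasonable, product not ruled out | *Possibly*: one criterion is enough | Triggered |
| Harm after injection, not explained by the subject's condition or environment, that follows the procedure in time or fits its known pattern | *Probably*: these criteria name the procedure | Triggered |
| Harm after injection that the investigator considers readily explained by another therapy, such as surgery or anesthesia | *Unlikely*, if so rated | Not triggered |

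The first and last rows are the gap.

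**2. What the other provisions supply**

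The 24-hour SAE form, the reports to DSMB and FDA, and the review of all adverse events give notice. The urgent-measures sentence in 9.4.1 is permissive. The Sponsor's response to the DSMB follows a recommendation, so it depends on one being made. None of these is a required pause. The escalation gate is a required pause with no attribution limit, but it operates only between the groups.

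**3. Exposure after an event**

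Inputs: 5 subjects in Dose Group 1 and 10 in Dose Group 2 (Synopsis).

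- Dose Group 2, event in subject k: 10 − k injections remain, so 9, 8, …, 0. The mean is 45/10 = 4.5 if each subject is equally likely to have the event (assumption).
- Dose Group 1: 5 − k remain, so 4 to 0, before the DSMB gate applies.

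**4. Dose Group 2 dosing span against required DSMB meetings**

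Inputs: 14-day minimum spacing, stated per site after the first two subjects in Protocol 3.2 and without a site qualifier in Protocol 7.3 and SAP 3.2.3; DSMB meetings at least annually during enrollment (9.4.1).

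- One site, or study-wide spacing: 9 × 14 = 126 days.
- Two sites (assumed) under 3.2: one site injects on days 0, 14, 28, 42, 56 and 70, the other on days 14, 28, 42 and 56. That is 6 + 4 = 10 subjects in 70 days.

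Both are below 365 days, so all ten could be injected between two required meetings.

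**5. Notice before the next injection**

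- 14-day spacing less 1 day for the SAE form: 14 − 1 = 13 days.
- Planned average pace, from the Synopsis durations: (3.5 − 2.0) × 365 / 15 = 36.5 days per injection, less 1 day = 35.5 days.

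With per-site spacing at more than one site the interval can be shorter. That is a property of the spacing rule, applies equally to product-related events, and would not be cured by a wider halt. At the intervals computed here the Sponsor would know before the next injection. What is missing is a rule requiring it to wait.

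**The case against.** The strongest reply is that 8.6 already draws most procedural harm into the product rating. *Possibly related* can be met by timing alone, even where a link seems unlikely, and two of the *probably related* criteria refer to the procedure. This stands, and it is why the gap is narrow. It does not close the gap: harm before injection cannot satisfy the timing criterion, and the *unlikely* category expressly allows for events explained by other therapy.

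Second, the primary objective in 2.1 is the safety of subretinal administration of AAV2-hCHM in a dose escalation, not of the surgery alone. Protocol 3.1 says the surgery resembles that of the earlier RPE65 studies. Tying dose decisions to the product is defensible. This also stands, and it is the reason to leave the DLT and MTD rules alone. It does not explain why a halt for death should depend on the same attribution.

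Third, the DSMB sees everything and can act at any time. That is correct as far as it goes, but it describes discretion.

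A reader might infer that a procedural death would bring no response, or that nobody would look for a year. The documents do not support either reading. SAE forms are due within 24 hours, the DSMB reviews all adverse events, and annual meetings are a minimum. The DSMB guidelines, the detailed monitoring plans and the Manual of Procedures are not in the file and may already contain a hold.

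**Conclusion.** The point holds in a limited form. As written, the halt in 7.4 does not cover death or Grade 4 harm that occurs before any vector is given, or surgical or anesthetic harm rated *unlikely* to be product-related. For these, whether dosing pauses rests on Sponsor or DSMB discretion. This matters chiefly within Dose Group 2, where up to nine injections could follow with no internal gate; in Dose Group 1 up to four could follow before the gate.

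The frequency of such events cannot be stated, because the documents give no rate; 9.4.2 calls them rare. The conclusion assumes that the documents not in the file add no step. Section 9.4.2 was updated with risks seen so far, so dosing has begun and may be finished. If it is finished, the wording matters for any further dosing under 7.4 and for the second-eye study contemplated in 3.1.

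Severity is minor to moderate. The text does not support a finding that the dose-escalation rules are unsound or that procedural harm goes unmonitored.

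**What to change.** In the Grade 4/death sentence of Protocol 7.4, extend the attribution from AAV2-hCHM to *AAV2-hCHM or the vector administration procedure, including anesthesia*. Confirm against the toxicity table in the Manual of Procedures that the General exclusion does not remove anesthetic harms such as seizure or coma.

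Leave the DLT definition and the two-subject MTD count tied to the product, so that dose-finding is unaffected. No new data are needed, because 8.6 already records the relationship to the procedure.

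The cost is a rare, short enrollment pause and a protocol amendment. Under 9.4.1, an amendment with safety implications needs IRB and DSMB approval and submission to the IND before it takes effect. If the DSMB guidelines already impose this hold, a cross-reference to them in 7.4 would be enough.

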## 7.5 Compliance and Adherence

Following the subretinal administration of AAV2-hCHM, subjects will be followed according to the protocol schedule of evaluations. Subjects will be encouraged to follow-up completely and according to the study endpoints. Non-adherence to the protocol will be reported to the relevant regulatory groups overseeing the study.

## 7.6 Accountability

Adequate records of investigational product receipt and disposition will be maintained by the investigational Pharmacy, and records of receipts, investigational drug orders, dispensing records, and disposition forms will be examined during the course of the study. The purpose of these records is to ensure the regulatory authorities and the Sponsor that the investigational new drug will not be distributed to any person who is not a study subject under the terms and conditions set forth in this protocol. The investigational product is to be prescribed by the

Investigators or qualified designee and may not be used for any purpose other than that described in the protocol. At study completion, all investigational product supplies including partially used and empty containers must be destroyed or returned to the Sponsor, or designee, per their instructions.

## 8 SAFETY MANAGEMENT

#### 8.1 Clinical Adverse Events

All adverse events will be monitored throughout the active and long-term follow-up phase following vector administration. Adverse event inquiry and assessment will be conducted on an ongoing basis during study participation through the following means:

- Subject inquiry or report
- Physical observation and/or physical examination
- Laboratory and any other diagnostic test results review
- Telephone call
- E-mail
- Postal query

The toxicity reporting scale (located in the Manual of Procedures) should be used, when possible, to assess adverse events.

#### 8.2 Adverse Event Reporting

All events described by the subject will be reported as AEs, regardless of toxicity grade in.

Protocol-defined safety laboratory test results will be collected prospectively and analyzed separately as part of the study. Additional laboratory test results at other time points may be available to the Investigators as part of standard clinical practice. Throughout the active phase of the study, laboratory-related abnormalities should be recorded as AEs only if considered clinically significant, outside the range of expected values given the subject's baseline assessments and clinical course, and not known to be part of another AE diagnosis. As per regulatory guidelines, pre-existing conditions, including abnormal lab values manifest at baseline testing, will only be reported as adverse events if the condition worsens in severity and/or frequency.

The Investigators will follow an AE until the event is either resolved or assessed as stable.

The Investigators are responsible for notifying the Sponsor representative or designee and the IRB of all AEs and other unanticipated problems related to research. Unanticipated problems are other types of incidents, experiences, and outcomes that occur during the conduct of human subject research that are not considered adverse events. For example, some unanticipated problems involve social or economic harm instead of the physical or psychological harm associated with adverse events. In other cases, unanticipated problems place subjects or others at increased *risk* of harm, but no harm occurs.

The Sponsor or designee will notify the appropriate federal regulatory authorities (FDA, NIH OBA, DSMB). Events that do not require expedited reporting will be summarized at the time of continuing review / annual report.

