## 4. GENERAL CONSIDERATIONS FOR DATA ANALYSIS

Due to the small sample size there are no statistical hypotheses regarding treatment effects. Rather, displays and comparisons of study results – regarding dose-related safety and efficacy among the dose cohorts – will primarily utilize descriptive statistics, as noted below.

Unless otherwise specified, continuous variables will be summarized by presenting the number of non-missing observations (n), mean, standard deviation, median, minimum, and maximum. Categorical variables will be summarized by presenting the number and percentage of subjects for each category.

Summary results will be provided for each dose cohort. All tabulations will be based on pooled data across study sites.

Analyses will be performed using SAS for Windows statistical software, version 9.2 or higher (SAS, Cary, NC), except where other software may be deemed more appropriate.

CTI will perform all efficacy and safety statistical analyses.

Subject data will be listed, sorted by dose cohort and subject number.

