### 4.3 Assessment Windows

For the purpose of listing and summarizing data, the time-in-study for each subject observation will be defined using study days. Such days will be measured relative to Day 0, the day in which the investigational product is received. Because protocol-specified visits (e.g., Day 30) will not necessarily occur on the same study day for all subjects, study visits will be defined through the use of windows. Study visits will have windows as per the following schema:

Spark Therapeutics AAV2-hCHM-101 Statistical Analysis Plan v3.0

Study Visit	Visit and Laboratory Testing Window
Study Day 0	Day of investigational product administration
Study Day 1	No window
Study Day 14	$14 \pm 2$ days
Study Day 30	$30 \pm 5$ days
Study Day 90	$90 \pm 30$ days
Study Day 180	$180 \pm 30 \text{ days}$
Study Day 365	$365 \pm 30$ days
Year 1.5	$547 \pm 30$ days
Year 2	730± 60 days

For evaluations after Year 2, the subject will go into the long-term follow-up phase. The subject returns to the clinic for follow-up at Years 2.5 and then annual follow-up, done in the clinic, for Years 3-5 for safety evaluations, standard ophthalmologic examinations, and retinal/visual function tests. The windows for the long-term follow-up visits are  $\pm$  60 days.

All data will be summarized by visit based on the visit in which the data was recorded in the database.

Baseline will be defined as the last pretreatment value during the screening period. If a repeat laboratory sample was drawn for a visit, only the repeat sample values will be listed or summarized. If there are repeated visual tests within the same visit, the average of all test results will be used for summary analysis. If there are more than one screening/baseline visit, the result from the later visit will be used for the analysis. Visual test results from all visits will be listed.

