## 7.3 Clinical Laboratory Assessments

Laboratory assessments for hematology with differential, serum chemistries, urinalysis, AAV viral capsid antibody, PBMC for ELISpot, and vector shedding will be performed in accordance to the Schedule of Assessments in Appendix A.

Laboratory values will be presented in the data listings.

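### A high-grade laboratory value not recorded as an AE enters no planned toxicity table by dose and has no written relatedness step for the DLT definition

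*Protocol*

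**What the plan says.** **Recording.** Protocol 8.2 states: "Protocol-defined safety laboratory test results will be collected prospectively and analyzed separately as part of the study". In the same paragraph, for the active phase, it adds that "laboratory-related abnormalities should be recorded as AEs only if considered clinically significant, outside the range of expected values". Expected values are judged against the subject's baseline and clinical course, and a third condition excludes abnormalities that belong to another AE diagnosis. All three conditions must hold. Toxicity grade is not among them.

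**Laboratory output.** SAP 7.3 ends: "Laboratory values will be presented in the data listings". The SAP 4 default, "Unless otherwise specified, continuous variables will be summarized by presenting the number of non-missing observations (n), mean" and the other usual statistics, gives way to specific instructions. SAP 4.3 adds: "If a repeat laboratory sample was drawn for a visit, only the repeat sample values will be listed or summarized".

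**Limiting toxicity.** Protocol 7.4 defines DLT as "any irreversible Grade 3 or higher toxicity, or any reversible Grade 4 toxicity" that is possibly or probably related to AAV2-hCHM. Toxicity lasting more than seven days counts as irreversible; toxicity resolving in seven days or fewer is reversible. On the scale: "The toxicity criteria are based on the WHO toxicity scale, with added assessments pertaining to ocular AEs". The scale itself is in the Manual of Procedures. The synopsis names limiting toxicity as the primary statistical endpoint.

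**Grade and causality.** Protocol 8.5 asks for the toxicity grade of an AE where applicable. Protocol 8.6 asks the investigator to document relatedness for each AE. SAP 7.2.5 tabulates treatment-emergent AEs by system organ class, preferred term and greatest intensity. The SAP contains no table by toxicity grade and no DLT output.

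**The concern.** Protocol 8.2 sets up two channels for laboratory safety: AE recording, which is filtered by judgement, and a separate analysis of the protocol-defined tests. The second channel should show what the first leaves out. The SAP reduces it to a listing of values, without grade, change from baseline or count by cohort.

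The DLT definition works on grade, duration and relatedness, and has no test of clinical significance. A laboratory value can therefore reach a DLT grade and still fail the 8.2 filter. At stake is the systemic part of the primary safety question. The report could present its AE tables by dose while high-grade laboratory values sit ungraded in a listing, or are missing from it because a repeat was drawn. In an open-label trial, whether such a value is counted would rest on an investigator's judgement that the DLT definition does not ask for.

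**Working it through.** The documents give no figure to reproduce on this point, so the main check follows a Grade 3-4 laboratory value through the written rules.

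**1. Two paths after Protocol 8.2**

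| What is needed | Value passes the filter | Value fails the filter |
|---|---|---|
| AE record | Yes | No |
| Toxicity grade | Noted where applicable (8.5) | No grading step written in protocol or SAP; Manual of Procedures not available to check |
| Relatedness | Documented (8.6) | No written step |
| Table by dose cohort | AE table, by intensity (SAP 7.2.5) | None |
| Listing | AE and laboratory listings | Laboratory listing, unless replaced by a repeat (SAP 4.3) |
| DSMB | Both (SAP 8) | Laboratory listing only |

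**2. Does a general clause supply the missing table?** SAP 4 summarises continuous variables unless told otherwise, and SAP 7.3 tells otherwise. SAP 4.3 also says that data are summarised by visit, but that sentence settles which visit label applies. Even on the generous reading, the result would be means by visit. A mean does not show how many subjects reached Grade 3 or 4.

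**3. The repeat rule against the seven-day rule.** Reversibility needs at least two values in time: the abnormal one and a later one. SAP 4.3 keeps one per visit. If a related Grade 4 value is followed by a repeat for the same visit that shows recovery within seven days, the event meets the 7.4 definition as reversible Grade 4. The value that qualifies it is then absent from the listing.

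**4. Comparison with other safety data.** SAP 7.4 lists ophthalmic findings with a grade of 1-4 and their relationship to the procedure and product. SAP 7.6 tabulates normal and abnormal physical findings by cohort. Laboratory tests get neither treatment.

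**5. Size**

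- Hematology and chemistry are scheduled at 10 post-injection visits (Days 1, 3, 14, 30, 90, 365; Years 2, 3, 4, 5): 15 × 10 = 150 panels. Through Day 30 in Dose Group 1: 5 × 4 = 20 panels.
- One subject is 1/5 = 20% of Dose Group 1 and 1/10 = 10% of Dose Group 2.
- Two subjects with limiting toxicity in a dose group define the maximum tolerated dose (7.4). Let p be the true DLT probability and c the share of DLTs recognised; both are assumed, since the documents give neither. With q = p × c, P(at least 2) = 1 − (1 − q)^n − n·q·(1 − q)^(n−1). Example: n = 5, p = 0.2, c = 1 gives 1 − 0.328 − 0.410 ≈ 0.263.

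| n | p | c = 100% | c = 75% | c = 50% |
|---|---|---|---|---|
| 5 | 0.1 | 0.081 | 0.048 | 0.023 |
| 5 | 0.2 | 0.263 | 0.165 | 0.081 |
| 5 | 0.3 | 0.472 | 0.315 | 0.165 |
| 5 | 0.4 | 0.663 | 0.472 | 0.263 |
| 10 | 0.1 | 0.264 | 0.170 | 0.086 |
| 10 | 0.2 | 0.624 | 0.456 | 0.264 |
| 10 | 0.3 | 0.851 | 0.695 | 0.456 |
| 10 | 0.4 | 0.954 | 0.851 | 0.624 |

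This shows only that a two-subject rule is sensitive to under-recognition. It does not estimate the loss here, because laboratory events are one part of all DLTs and no miss rate can be derived.

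**The case against.** A reader might infer that such a value can never be graded or reach DLT assessment. The documents do not support that. Protocol 7.4 defines DLT on toxicity, not on AE status, and ties the toxicity scale to the stopping rules. Protocol 8.1 names laboratory review as a means of AE assessment, 8.3 includes laboratory observations among AEs, and SAP 8 sends the listings to the DSMB. The Manual of Procedures may also contain a grading or review step.

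The filter also overlaps with the relatedness requirement. A value expected from the clinical course would often be judged unlikely to be related. One that belongs to another diagnosis is captured through that AE, and a baseline abnormality that worsens can be reported. What remains is mainly a new, unexpected, possibly related value that the investigator calls not clinically significant. This narrows the gap. It does not close it, because for that value the relatedness judgement is never required in writing.

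Listings may be enough for 5 and 10 subjects with no hypothesis tests, and the SAP revision table shows that the listing wording was deliberate. This has force for the escalation review, where 20 panels can be read line by line. It has less for a final report on 150 panels, and none for an original value that is no longer listed.

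Two inferences should not be drawn. Protocol 8.2 sets the separate analysis beside the filter but does not make it the reason for the filter. The filter is worded for the active phase only, and Protocol 4.5 asks for all AEs in long-term follow-up, so the Year 3-5 tests are not evidence of exclusion.

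**Conclusion.** The point holds in a limited form. A Grade 3-4 laboratory value that fails the Protocol 8.2 filter appears in no planned laboratory toxicity table by dose cohort, can leave the listing if the sample is repeated, and has no written step that provides the relatedness assessment required by Protocol 7.4. Its route to DLT review is unspecified, not closed.

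The unit of error is one subject, 20 or 10 percentage points of a cohort's laboratory toxicity rate. The expected number of such subjects cannot be derived. The conclusion assumes that the toxicity scale covers laboratory tests, which is likely because it is WHO-based, and that the Manual of Procedures does not already supply the missing step. Neither could be checked. This is a worthwhile, cheap correction to a primary safety analysis; it does not show that toxicity has been or will be missed.

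**What to change.** 1. **SAP 7.3 and 4.3.** Grade all post-baseline hematology and chemistry values, and urinalysis where the scale covers it, on the existing Manual of Procedures scale. Include originals that were followed by a repeat, and list both values. Tabulate worst post-baseline grade and shift from baseline by dose cohort as n/N. Flag Grade 3 or higher in the DSMB output.
2. **Protocol 8.2 and 8.6.** For any laboratory value of Grade 3 or higher that is worse than baseline, require a documented relatedness assessment whether or not it is recorded as an AE, in both the active and long-term phases. The 7.4 definition stays as it is and can then be applied to these values.

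The repeat-sample change is essential: without it, a worst-grade table would lose the values it is meant to show. The cost is one programmed grading step, one or two tables, short text changes in both documents and a few more relatedness assessments. No new tests or visits are needed.
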